3.3 Patient Data and Study Conduct

3.3.1 *Patient Disposition*

Counts and percentages of patients who were screened (signed informed consent), terminated prematurely during screening (screen failures), received run-in treatment, completed run-in period, and randomised will be summarized in total based on all screened patients.

Counts and percentages of patients in each of the following categories will be presented by treatment arm and in total for the ITT set, FAS and PP set:

- Patients who were randomised

- Patients who received IMD
- Patients who completed the treatment period
- Patients who early discontinued the treatment period
- Patients who completed the study
- Patients who early discontinued from the study

Summary will also be provided for the Safety set [REDACTED]

For patients who discontinued early from treatment and from the study, primary reasons for premature discontinuation will also be summarized.

A summary of the number of patients who attended each scheduled visit will be presented.

Corresponding listings for disposition and visit attendance be produced.

[REDACTED]

3.3.3 Analysis Sets

Counts and percentages of patients in each analysis population will be summarized by treatment and in total based on the ITT set. Reasons for exclusion from the PP set will also be summarized.

Corresponding listing for analysis sets will be produced.

3.3.4 Demographic and Baseline Characteristics

The following demographic characteristics will be summarized by treatment and in total for the ITT set, the FAS and the PP set:

- Age at screening (in years)
- Age category (at screening)
 - < 65 years
 - \geq 65 to < 85 years
 - \geq 85 years
- Sex (female, male)

[REDACTED]

The following history of dry eye disease will be summarized by treatment and in total for the ITT set, the FAS and the PP set:

- localisation (one eye, both eyes),

- time from first diagnosis to randomisation (in years):

3.3.5 *Medical History*

Medical history data are coded to SOC and PT using the Medical Dictionary for Regulatory Activities (MedDRA) version 26.0 or higher. Counts and percentages of patients with medical history by SOC and PT will be summarized by treatment and in total based on the Safety set, separately for ocular and systemic (non-ocular) [REDACTED]

3.3.6 *Historical Surgeries/Procedures*

Historical surgeries and procedures are coded to SOC and PT using the MedDRA version 26.0 or higher. Counts and percentages of patients with historical surgeries and procedures by SOC and PT will be summarized by treatment and in total based on the Safety set, separately for ocular and systemic (non-ocular).

[figure not shown]
3.3.7 Prior and Concomitant Medications

Prior and concomitant medications are coded to Anatomical Therapeutic Chemical (ATC) class and PT using the World Health Organisation Drug (WHODrug) dictionary (version Mar 2023G B3).

3.3.8 Study Medical Device Exposure and Compliance

The extent of exposure and compliance of patients to IMD will be summarized by treatment group for the FAS, PP set and Safety set [REDACTED]

Counts and percentages of patients treated for one single eye and for both eyes will be summarised.

IMD administration and compliance data will be listed.

3.4 Performance Assessment

The FAS will be the primary population for performance analysis. The PP set will be considered as secondary population and will be used for sensitivity analyses of the primary endpoint [REDACTED]

For primary [REDACTED] performance endpoint [REDACTED], descriptions will be given by treatment group at each assessment time. Change from baseline will be also presented, when applicable.

When using inferential analysis, Least Square (LS) means and its standard errors will be displayed for each treatment group. The LS means for the difference (T2769 - Vismed® Multi) between the treatment groups' change from baseline, its two-sided 95% CI and the p-value, when applicable, will be provided.

3.4.1 Primary Performance Endpoint

The primary objective is to demonstrate the non-inferiority of T2769 compared to Vismed® Multi in terms of total ocular surface staining (Oxford score) after 35 days of treatment. The primary

performance endpoint is the change from baseline (D1) in total ocular surface staining assessed on Oxford 0-15 scale, in the study eye at the D36 visit. [REDACTED]

[REDACTED]

[REDACTED]

Primary Analysis

The inferential analyses of the primary performance endpoint will aim to assess the non-inferiority of T2769 to Vismed® Multi.

The hypothesis of non-inferiority of T2769 compared to Vismed® Multi will be tested by calculating the bilateral 95% CI of the difference between groups (T2769 – Vismed® Multi) of the total ocular surface staining (Oxford score) at D36 in the study eye in the FAS.

The non-inferiority of T2769 to Vismed® Multi on the total ocular surface staining (Oxford score) will be primarily tested using an MMRM approach.

The model will include treatment and scheduled visit time points (D15 and D36) as fixed factors, patient as random factor, and baseline total ocular surface staining (Oxford score) as continuous covariate. Treatment by scheduled visit time point and baseline total ocular surface staining (Oxford score) by scheduled visit time point will be included as interaction terms in the model. [REDACTED]

[REDACTED]

[REDACTED]

[REDACTED]

[figure not shown]
[REDACTED]

LS means and corresponding standard errors for change from baseline at each analysis visit will be provided for each treatment group. The difference in LS means between T2769 and Vismed® Multi, corresponding standard error, and the two-sided 95% CI for treatment effect (difference T2769 - Vismed® Multi) will be estimated at each analysis visit in this model. Non-inferiority will be achieved if the upper bound of the two-sided 95% CI for the difference between treatment groups (T2769 - Vismed® Multi) at D36 is lower than the margin of 2 points.

Descriptive summary statistics on the values and changes from baseline will be presented for the total ocular surface staining (Oxford score) at each analysis visit by treatment group.

The mean and associated SD of the Oxford score in the study eye will be graphically displayed for each treatment by analysis visit in the FAS.

[REDACTED]

[figure not shown]

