6.1.2 Description of the Measures to be Taken to Minimize or Avoid Bias

6.1.2.1 Randomisation

A randomised design has been chosen to ensure a balanced allocation to the assignment of device arms of all patient's known and unknown characteristics. Randomisation helps to avoid possible bias in the selection and allocation of patients arising from the predictability of device assignments.

The randomisation code list stratified by site and lists of IMDs numbers for the packaging is generated by the Interactive Web Response System (IWRS) provider. Patients will be randomised on a 1:1 basis to T2769 or Vismed® Multi respectively.

Randomisation list(s) and lists of IMDs numbers for the packaging are to be kept in security by the editor (IWRS provider) according to their procedures.

The packaging list is to be kept by the company responsible for manufacturing and labelling of the treatment unit.

The randomisation and the IMD kit number will be allocated to the patients according to randomisation list using an Interactive Response Technology (IRT).

Randomisation will occur at Randomisation visit (Day 1; Visit#2) after all procedures have been performed and eligibility for the investigation confirmed. The patient who meets the eligibility criteria will be randomly assigned to treatment and associated to a randomisation number.

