6.1.7 Investigation Sites

Patients are to be enrolled in approximately 40 investigational sites in 9 countries.

The Sponsor will maintain an updated list of Principal investigators and investigation sites, separately from this CIP, throughout the duration of the clinical investigation. The definitive list will be provided with the CIR.

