6.3.8 Number of Patients Required to be Randomised in the Clinical Investigation

It is planned to randomise 250 patients in order to have 226 evaluable patients (113 per group) for the FAS analysis.

Evaluable patients will be defined as randomised patients having received at least one dose of IMD and with at least one performance endpoint post-randomisation visit.

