7.2.1 Performance Analyses

Primary performance endpoint [REDACTED] will be primarily analysed on the FAS. Sensitivity analysis of the primary [REDACTED] endpoints will be performed on the PP.

For primary [REDACTED] performance variables, descriptions will be given by treatment group at each assessment time. Change from baseline will be also presented, when applicable.

When using inferential analysis, least square (LS) means and its standard errors will be displayed for each treatment group. The LS means for the difference (T2769 - Vismed® Multi) between the treatment groups' change from baseline, its 95% confidence interval (CI) and the superiority p-value, when applicable, will be provided.

Primary [REDACTED] performance

Objective

The primary objective is to demonstrate the non-inferiority of T2769 compared to Vismed® Multi in terms of total ocular surface staining (Oxford score) after 35 days of treatment [REDACTED]

Variables

The primary performance variable is change from baseline (D1) in total ocular surface staining grade according to Oxford 0-15 grading scheme at D36 in the study eye. The total ocular surface staining (Oxford score) is defined as the sum of corneal, temporal, and nasal staining scores.

Primary analysis

[figure not shown]
The inferential analyses of the primary performance variable will aim to assess the non-inferiority of T2769 to Vismed® Multi. The hypothesis of non-inferiority of T2769 compared to Vismed® Multi will be tested by calculating the bilateral 95% CI of the difference between groups (T2769 – Vismed® Multi) of the total ocular surface staining (Oxford score) at D36.

The non-inferiority of T2769 to Vismed® Multi on the total ocular surface staining (Oxford score) will be primarily tested using a Mixed Model for Repeated Measures (MMRM) approach. The model will include treatment and scheduled visit time points (D15 and D36) as fixed factors, patient

as random factor, and baseline total ocular surface staining (Oxford score) as continuous covariate. Treatment by scheduled visit time point and baseline total ocular surface staining (Oxford score) by scheduled visit time point will be included as an interaction term in the model.

The 95% CI for treatment effect (difference T2769 - Vismed® Multi) will be estimated at D36 in this model. Non-inferiority will be achieved if the upper bound of the 95% CI for the difference between treatment groups (T2769 - Vismed® Multi) is lower than the margin of 2 points.

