7.10 MANAGEMENT OF POTENTIAL CONFOUNDING FACTORS

Baseline value will be included in all MMRM models (if applicable) as covariate.

Other covariates will be explored and detailed in the SAP.

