7.15 PROCEDURES FOR REPORTING ANY DEVIATION(S) FROM THE ORIGINAL STATISTICAL PLAN

Any changes from the planned analyses will be described and justified in the SAP and the final clinical investigation report.

7.17 DEFINE A STRATEGY FOR POOLING DATA, IF APPLICABLE.

Not applicable.

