2.2 Study Design

2.2.1 *Overview*

This investigation consists in a 5-week, international, multicentre, randomised, investigator-masked, 2-parallel-group (T2769 versus Vismed® Multi) confirmatory clinical investigation, planning to randomise 250 patients.

The investigation period for a patient is split into two parts, with a total maximum duration of 49 days:

- 7 to 10 days of run-in period with preservative-free artificial tears (Hydrabak®, NaCl 0.9%)
- 36 to 39 days of treatment period with the Investigational Medical Device (IMD): either T2769 or Vismed® Multi.

Four visits are scheduled during the course of the investigation:

- Visit #1: Day 1-10/Day 1-7: Screening visit (run-in period)
- Visit #2: Day 1: Randomisation visit (D1)
- Visit #3: Day 15 (± 1 day): (D15)
- Visit #4: Day 36 (+3 days): Final or premature discontinuation visit.

The detailed Schedule of Visits and Procedures is described in Table 2 of the CIP [REDACTED]

2.2.2 *Randomisation and Masking*

Patients are randomised stratified by site on a 1:1 basis to T2769 or Vismed® Multi respectively. The randomisation code list and the lists of IMDs numbers for the packaging is generated by the Interactive Web Response System (IWRS) provider, the randomisation and the IMD kits numbers are allocated to the patients according to randomisation list using an Interactive Response Technology (IRT).

Randomisation occurs at Randomisation visit (Day 1; Visit #2) after all procedures have been performed and eligibility for the investigation confirmed.

This is an investigator-masked clinical investigation, a double-masked investigation design not being possible due to different commercial packaging between T2769 and Vismed® Multi.

The masked investigator remains masked to the IMD (T2769 or Vismed® Multi). The masked investigator does not receive the returned IMDs from the patients.

The following-up of returned IMDs is delegated to an unmasked collaborator throughout the clinical investigation. The unmasked collaborator is in charge of recording the used/unused IMDs.

Masking is achieved by coding the interventions, providing each product unit with identical cardboard box and by identifying it by an IMD kit number.

The code should not be broken except:

- in case of medical emergency (where knowledge of the IMD received would affect the treatment of the emergency),
- or when it is a regulatory requirement (e.g., for Unanticipated Serious Adverse Device Effect [USADE]).

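### Randomisation is stratified by site but no site term is visible in the primary MMRM; if arms are balanced within site and sites still differ after baseline adjustment, the 95% CI is slightly too wide (conservative)

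*SAP*

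**What the plan says.** Both documents stratify the allocation by site and name no other stratum. Protocol 6.1.2.1: "The randomisation code list stratified by site and lists of IMDs numbers for the packaging is generated" by the IWRS provider. SAP 2.2.2: "Patients are randomised stratified by site on a 1:1 basis to T2769 or Vismed® Multi respectively". Neither says how balance within a site is obtained, and no block is mentioned.

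Protocol 6.1.7 gives the number of sites: "Patients are to be enrolled in approximately 40 investigational sites in 9 countries". Protocol 6.3.8 gives the sample size: "It is planned to randomise 250 patients in order to have 226 evaluable patients (113 per group) for the FAS analysis".

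The model is described in SAP 3.4.1: "The model will include treatment and scheduled visit time points (D15 and D36) as fixed factors, patient as random factor, and baseline" Oxford score as a continuous covariate. Protocol 7.2.1 has the same terms and adds: "Treatment by scheduled visit time point and baseline total ocular surface staining (Oxford score) by scheduled visit time point will be included". The protocol's model paragraph has no redaction in it. In the SAP, redacted text begins directly after the list.

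Protocol 7.10 leaves room for more terms: "Other covariates will be explored and detailed in the SAP". The visible SAP text names none, and the visible part of SAP section 6 (changes from the CIP) does not mention site.

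**The concern.** When arms are balanced within site, differences between sites largely cancel out of the treatment comparison. A model without site still counts those differences as error, so it reports a standard error larger than the real sampling error of the estimate. The decision rule compares the upper limit of the two-sided 95% CI at D36 with 2 points, so a wider interval makes non-inferiority slightly harder to show.

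Site differences are plausible here. The endpoint is a slit-lamp score graded by an examiner, it is collected in 9 countries, and the protocol keeps the same examiner and slit lamp for a patient across visits. What is at stake is a little reported precision and a foreseeable question about why the only stratum does not appear in the analysis. The validity of the non-inferiority claim is not at stake.

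**Working it through.** **Inputs from the documents.** 250 randomised, 226 evaluable (113 per group), about 40 sites, 1:1 allocation stratified by site, model terms as listed.

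- Patients per site: 250/40 = 6.25 randomised and 226/40 = 5.65 evaluable.
- Implied loss: (250 − 226)/250 = 9.6%.

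**Assumptions.** The adjusted site ICC (the share of the baseline-adjusted variance that lies between sites), block size, spread of site sizes and D15-D36 correlation (0.6) are not in the documents. The SD is not visible either, so results are given as ratios, which do not depend on it.

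**Step 1: limiting case.** With exact balance within every site, reported SE / true SE = 1/√(1 − ICC), and the one-sided error at the margin is Φ(−1.96/√(1 − ICC)).

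- ICC 0.05: 1/√0.95 = 1.026; error 0.0222
- ICC 0.10: 1/√0.90 = 1.054; error 0.0194
- ICC 0.20: 1/√0.80 = 1.118; error 0.0142

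**Step 2: realistic balance.** The setting was 40 unequal sites, incomplete last blocks, 24 of 250 lost at random, and the planned two-visit model. The exact variance of the D36 contrast was averaged over 3,000 designs (total SD set to 1).

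| Adjusted ICC | Reported SE, blocks of 4 | True SE | Ratio, blocks of 4 | Ratio, blocks of 2 | Ratio, blocks of 6 | Ratio, unblocked |
|---|---|---|---|---|---|---|
| 0 | 0.1334 | 0.1334 | 1.000 | – | – | 1.000 |
| 0.02 | 0.1334 | 0.1324 | 1.008 | 1.008 | 1.007 | 1.000 |
| 0.05 | 0.1333 | 0.1308 | 1.019 | 1.021 | 1.018 | 1.000 |
| 0.10 | 0.1332 | 0.1281 | 1.040 | 1.043 | 1.037 | 1.000 |
| 0.20 | 0.1330 | 0.1226 | 1.085 | 1.092 | 1.078 | 1.000 |

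A separate two-visit simulation (6,000 runs per case, blocks of 2 and 4) gave ratios of 1.017-1.020, 1.036-1.039 and 1.074-1.096 at ICC 0.05, 0.10 and 0.20. One-sided error was 0.023-0.024, 0.020-0.022 and 0.015-0.019. The direction and size agree.

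**Step 3: effect of the remedy.** REML fits, two visits, blocks of 4, 6,000 trials per case, without versus with a random site intercept:

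| Adjusted ICC | CI width, without / with | Empirical SD of estimate, without v with | One-sided error, without v with |
|---|---|---|---|
| 0 | 1.005 | 0.1312 v 0.1312 | 2.2% v 2.3% |
| 0.02 | 1.011 | 0.1311 v 0.1312 | 2.5% v 2.5% |
| 0.05 | 1.022 | 0.1302 v 0.1301 | 2.4% v 2.6% |
| 0.10 | 1.045 | 0.1301 v 0.1294 | 2.3% v 2.8% |
| 0.20 | 1.102 | 0.1232 v 0.1212 | 1.9% v 2.6% |

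The Monte Carlo SE of the error rates is about 0.2 percentage points. The 0.5% at ICC 0 arises because the site variance cannot be estimated below zero; it is not a real gain. A separate single-visit REML simulation gave 1.2%, 2.2%, 4.6% and 10% extra width at ICC 0.02, 0.05, 0.10 and 0.20, with two-sided error near 5% when site was included.

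Fixed site effects do less well with so few patients per site. In a single-visit simulation (blocks of 4 or 6) the interval without site was 0.989-1.007 times as wide as with fixed sites at ICC 0.05, and 1.014-1.034 times at 0.10.

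**Step 4: which ICC is plausible.** Suppose a site's grading shift persists from baseline to D36, with raw ICC ρ and within-site correlation r between baseline and D36. With b = ρ + r(1 − ρ), the adjusted ICC is ρ(1 − b)/(1 + b).

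- ρ = 0.10, r = 0.3: b = 0.37, so 0.10 × 0.63/1.37 = 0.046. With r = 0.7: 0.016.
- ρ = 0.30, r = 0.3: b = 0.51, so 0.30 × 0.49/1.51 = 0.097. With r = 0.7: 0.035.

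Under that model the adjusted ICC is about 0.02-0.10, and 0.20 is less plausible.

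**The case against.** The strongest objection is that a site term may already be in the plan. Protocol 7.10 defers covariates to the SAP, the redaction in SAP 3.4.1 starts exactly where such terms would be listed, and SAP 3.1.2, 3.1.4 and 3.1.6 are missing from the visible text. This stands. A reader might infer that site was left out of the analysis; the documents show only that it is absent from the visible text.

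The second objection is that the effect needs two facts the documents do not give: balance within site, and site differences that survive baseline adjustment. This stands too. Stratifying a list by site makes blocking likely, but that is an inference. The ICC range in Step 4 is also only indicative, because the protocol fixes the examiner per patient and not per site.

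The third objection is that the estimate gains almost no precision: its empirical SD falls by 0.1% at ICC 0.05 and 0.5% at 0.10. This is correct. What the site term mainly changes is the reported interval, which then matches the sampling error that the allocation already delivers. Leaving site out with about 6 patients per site is defensible.

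Two stronger readings are tempting. One is that ignoring the stratum makes the test invalid or too liberal. The calculations show the opposite direction, with one-sided error at or below about 2.5%. The other is to convert the extra width into Oxford points or a gain in power. That needs an SD, and the SD and the hypothesis that drives the sample size are not visible (SAP 2.2.4 and protocol 7.11 are partly redacted), so no such figure is given.

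**Conclusion.** The point holds as a minor, conditional one. No site term is visible, and site is the only named stratum. With allocation balanced within site and an adjusted ICC of 0.05 to 0.10, the planned interval is about 2% to 5% too wide. The excess would reach roughly 8-10% at 0.20, which is less plausible, and is nil if allocation is unblocked or sites do not differ after adjustment. The error is conservative, the treatment estimate hardly moves, and the non-inferiority decision would rarely change. The size rests on assumed ICC, block size, site sizes and visit correlation; the direction needs only balance within site and residual site differences. Confidence is medium because of the redaction and the unstated blocking.

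**What to change.** First check whether the redacted part of SAP 3.4.1 already contains site. If it does, nothing more is needed.

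If it does not, then before database lock:

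- Add site as a random intercept to the primary MMRM in SAP 3.4.1 and to the per-protocol analysis of the same endpoint. A random term is preferable to about 40 fixed effects, which recover little here.
- Record it in SAP section 6 as a change from the CIP. Protocol 7.10 assigns covariates to the SAP, and protocol 7.15 gives the reporting route: "Any changes from the planned analyses will be described and justified in the SAP and the final clinical investigation report".
- State in SAP 2.2.2 whether allocation is blocked within site; the block size need not be given. If it is not blocked, the planned standard error is already right and the term is optional.
- If site is left out on purpose, one sentence with the reason is enough.

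The cost is one SAP line and one model term, with no new data and no more patients. The only downside is one more variance parameter; if it is estimated at zero, the model reduces to the planned one.

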7.11 DESCRIPTION OF PROCEDURES FOR MULTIPLICITY CONTROL AND ADJUSTMENT OF ERROR PROBABILITIES

The overall alpha (family-wise error rate) will be maintained at the one-sided α -level of 0.025 by using the following testing strategy: [REDACTED] to demonstrate that T2769 is non-inferior (according to a pre-defined non-inferiority margin of 2 points in the total Oxford grade) to Vismed® Multi in patients with moderate to severe dry eye syndrome as assessed by the total ocular surface staining grade change from baseline to D36 in the study eye, [REDACTED]

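### Does treating patient as a random factor force equal variances at D15 and D36, and so spoil the decisive D36 confidence interval?

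*SAP*

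**What the plan says.** SAP 3.4.1 states that non-inferiority "will be primarily tested using an MMRM approach". On the model terms it says: "The model will include treatment and scheduled visit time points (D15 and D36) as fixed factors". It then adds "patient as random factor, and baseline total ocular surface staining (Oxford score) as continuous covariate", with treatment-by-visit and baseline-by-visit interactions. Several redacted blocks and a removed figure come next, before the text resumes with the LS means. The treatment difference and its interval "will be estimated at each analysis visit in this model", and the criterion is that the upper bound "at D36 is lower than the margin of 2 points".

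Protocol 7.2.1 describes the same model, with patient "as random factor, and baseline total ocular surface staining (Oxford score) as continuous covariate", and goes from the interaction terms to the interval: "The 95% CI for treatment effect (difference T2769 - Vismed® Multi) will be estimated at D36 in this model". Protocol 7.11 says that the family-wise error "will be maintained at the one-sided α -level of 0.025".

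The visible text of both documents gives no residual variance structure, no within-patient covariance structure and no degrees-of-freedom method. The opening of protocol section 7 assigns detailed methods to the SAP.

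**The concern.** Many readers take a random patient factor to mean a random intercept plus one common residual variance. Over two visits that is compound symmetry, with a single variance for D15 and D36. The D36 interval would then borrow its width partly from D15, although the claim concerns D36 alone. If scores were less variable at D15 than at D36, the interval would be too narrow and the one-sided error would exceed 2.5%. If they were more variable at D15, the interval would be too wide and precision would be lost. Because one interval decides a confirmatory trial, this deserves a check. An unstructured covariance over two visits needs only one more parameter, which makes the simpler structure look like an avoidable weakness.

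**Working it through.** **Inputs from the documents.** Two post-baseline visits, margin 2 points and a two-sided 95% interval at D36 (SAP 3.4.1); one-sided alpha 0.025 (protocol 7.11); 113 evaluable patients per group (protocol 6.3.8). No SD, overall or by visit, is visible. The plan therefore has no coverage or variance figure to reproduce, and everything about the variance ratio below is an assumption.

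**Step 1: the unfavourable reading.** Let r = SD(D15)/SD(D36), where each SD is the residual SD after baseline adjustment at that visit. With complete data the D36 estimate is the same under either covariance structure; only its standard error changes. Under a common variance:

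- SE ratio (model/true): k = sqrt((r² + 1)/2)
- coverage = 2Φ(1.96k) − 1
- one-sided error at a true difference of exactly 2 points = Φ(−1.96k)

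For r = 0.8, k = sqrt((0.64 + 1)/2) = sqrt(0.82) = 0.906.

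| r (assumed) | k | coverage | one-sided error |
|---|---|---|---|
| 0.7 | 0.863 | 90.93% | 4.54% |
| 0.8 | 0.906 | 92.41% | 3.80% |
| 0.9 | 0.951 | 93.78% | 3.11% |
| 1.0 | 1.000 | 95.00% | 2.50% |
| 1.1 | 1.051 | 96.06% | 1.97% |
| 1.25 | 1.132 | 97.35% | 1.33% |

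A REML simulation agrees. It used 113 per arm and 1,500 runs per r, with assumed residual correlation 0.6, D36 SD 2.5 and 6% of D36 values missing. Coverage with a common variance was 92.8%, 94.5% and 97.5% at r = 0.8, 1 and 1.25. With an unstructured covariance it was 95.1%, 94.5% and 94.7%. The Monte Carlo standard error is about 0.6 points. The algebra is therefore right for that model.

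**Step 2: does a random patient factor imply that model?** Let b be the patient variance, and e15 and e36 the residual variances. Then

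- Var(D15) = b + e15
- Var(D36) = b + e36
- Cov(D15, D36) = b

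The variances are equal only if e15 = e36. The plan does not state that condition. Without it there are three free parameters, as many as in an unstructured 2×2 matrix. The two forms are equivalent whenever the covariance is non-negative and below both variances. The simulation's own case satisfies this: at r = 0.8 the SDs are 2.0 and 2.5, so the variances are 4 and 6.25 and the covariance is 0.6 × 2.0 × 2.5 = 3. That gives b = 3, e15 = 1 and e36 = 3.25, all positive. A random patient factor can therefore reproduce unequal visit variances exactly.

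**Step 3: if the redacted text specifies an unstructured residual.** With residual covariance c, the model has variances b + e15 and b + e36 and covariance b + c. Only these sums are identified. The D36 estimate and standard error depend only on the sums, so a redundant patient term leaves both unchanged. The coverage loss in Step 1 does not arise.

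**Step 4: effect on the bound.** In the simulated case r = 0.8, the mean standard errors were 0.306 (common variance) and 0.339 (unstructured). With the t quantile of 1.971, the upper bound moves by 1.971 × (0.339 − 0.306) = 0.07 points, against a margin of 2 points.

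**The case for a change.** The strongest reply rests on the protocol. In 7.2.1 no redaction mark stands between the interaction terms and the D36 interval, so the random-patient wording appears complete there. The visible entries in SAP section 6 list no change to this model. A pivotal trial should not let its type I error depend on an unstated equal-variance assumption when visit-specific variances cost one parameter with about 226 patients.

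Part of this stands. The visible wording is loose, and a reader cannot tell from it which covariance will be fitted. If the fitted model were a random intercept with constant residual variance, and the visit SDs differed clearly, the D36 interval would be miscalibrated as shown above.

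The rest does not. Silence in the protocol does not choose compound symmetry, because section 7 hands the detail to the SAP. The protocol section is itself visibly cut: the contents list places 7.2.1 on page 66 and 7.2.2 on page 69, yet little text remains, with redaction marks and a removed figure. A SAP that supplies the covariance would add detail to the protocol's model, so its absence from the list of changes shows nothing. Where the SAP text is blacked out, the content cannot be counted as missing from the plan.

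**Conclusion.** The concern does not hold. Equal variance at D15 and D36 follows only from a constant residual variance, and neither document states one. The SAP's covariance specification may lie in the redacted text directly after the model sentences. If that text specifies an unstructured residual, the patient term is merely redundant and the D36 result is unaffected.

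The possible harm is also unquantified. With no visit-specific SD visible, r could lie on either side of 1, and at r = 1 there is no effect. For SDs within 10% of each other, coverage would be about 93.8% to 96.1% even under compound symmetry. An error of 3.8% or more needs a D15 SD at or below 0.8 of the D36 SD, together with a true difference exactly at the margin. In the one simulated case at r = 0.8 (assumed D36 SD 2.5), the bound moves by about 0.07 points, which matters only if it falls very close to 2.

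What remains is a query: someone with the unredacted SAP can confirm in one line which within-patient covariance is fitted. That is a point of detail hidden from the public reader, and no error in the plan has been shown.
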